6.1. Subject Enrollment and Treatment Assignment

It is the responsibility of the investigator to ensure that subjects are eligible to participate in the study prior to enrollment and continue to remain eligible throughout the study.

Once the ICF has been obtained, all screening and admission tests and assessments have been assessed, and study eligibility has been confirmed, subjects will be enrolled to receive study drug on Day 1.

Subjects will receive the study treatments as described in Section 5.3.

Table 6-1. Schedule of Assessments

Study Procedure	Screen ^a	Day -1	Day 1	Day 2	Day 3	Day 4	Day 5	Day 6 ^b	Day 15 (±1) Follow-Up ^c	ET ^d
Written Informed Consent	X									
Medical History	X									
Complete Physical Exam	X	X						X	X	X
Symptom-Driven Physical Examination ^e			X	X	X	X	X			
Height	X									
Weight	X	X								
Vital Signs ^f	X	X	X	X	X	X	X	X	X	X
HIV-1, HBV, and HCV Testing	X									
Hematology ^g	X	X	X		X			X	X	X
Coagulation	X	X	X		X			X	X	X
Chemistry ^h	X	X	X	X	X			X	X	X
Urinalysis	X	X	X	X	X			X	X	X
Serum Pregnancy Test ⁱ	X	X						X	X	X
Creatinine Clearance	X	X								
Urine Drug and Alcohol Screen	X	X								
12-Lead ECG	X	X	X					X	X	X
Study Drug Administration			X							
Intensive Plasma PK ^j			X	X	X	X	X	X		
Urine PK ^k			X	X	X	X	X	X		

Study Procedure	Screen ^a	Day -1	Day 1	Day 2	Day 3	Day 4	Day 5	Day 6 ^b	Day 15 (±1) Follow-Up ^c	ET ^d
Review Study Restrictions	X	X						X	X	
Clinic Confinement		X	X	X	X	X	X			
Review AEs & Concomitant Medications ^l	X	X	X	X	X	X	X	X	X	X

- a Prospective subjects should be screened no more than 28 days prior to administration of the first dose of study drug.
- b Subjects will be discharged from the clinic on Day 6, following all morning assessments.
- c 14(± 1) days after the last administration of study drug, all subjects will return for an in-clinic follow-up visit and complete procedures as outlines.
- d Assessments will be performed within 72 hours of early termination from the study.
- e Symptom-driven PEs will be performed during confinement as needed, based on reported signs and symptoms.
- f Vital signs include blood pressure, heart rate, respiration rate, and temperature.
- g Hematology: CBC with differential.
- h See Section 6.9.5 for specifics.
- i Females of child-bearing potential only.
- j Intensive PK sampling will occur relative to the morning dosing of GS-9876 at the following time points:

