6.2. Pretreatment Assessments

6.2.1. Screening Visit

Prospective subjects should be screened no more than 28 days prior to administration of the first dose of study drug. If a subject does not begin the treatment phase within this 28-day window, all screening evaluation procedures must be repeated. Screening laboratory assessments may be repeated once within 28 days prior to administration of study drug to rule out laboratory error.

A sufficient number of subjects will be screened to identify planned number of subjects for enrollment.

Subjects should be instructed to fast (no food or drink, except water), starting from midnight (00:00) or earlier, as appropriate, on the evening prior to the screening visit to ensure an approximate 8-hour fast prior to the fasted blood sample collection the next morning.

Written informed consent must be obtained from each subject before initiation of any screening procedure. After a subject has provided informed consent, the investigator and other study personnel will determine if the subject is eligible for participation in the study. This assessment will include a review of the inclusion/exclusion criteria and completion of all screening procedures as outlined in [Table 6-1](#) and described in the following text.

Eligible subjects meeting all of the inclusion criteria and none of the exclusion criteria will be instructed on all protocol requirements, including the restrictions on concomitant medication usage and other substances as well as consumption of food or beverages containing alcohol, caffeine, or xanthine. Subjects will be asked to arrive at the study center on Day -1 for admission assessments.

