6.9.6. Creatinine Clearance and Estimated Glomerular Filtration Rate

Weight will be collected at screening and upon admission to calculate creatinine clearance (CL_{cr}) and estimate glomerular filtration rate (eGFR), however CL_{cr} will be used for inclusion criteria.

$$eGFR \text{ (mL/min/1.73 m}^2\text{)} = 175 \times (*S_{cr})^{-1.154} \times (\text{Age})^{-0.203} \times (0.742 \text{ if female}) \times (1.212 \text{ if African American})$$

* S_{cr} – serum creatinine

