**Figure 1-1. Study Design**

The categorization of renal impairment is based on creatinine clearance (CLCr) using the Cockcroft-Gault formula from the screening visit. Specifically, a subject will be considered as having

[figure not shown]
- Mild impairment if CLcr (rounding to the nearest integer) is 60-89 mL/min
- Moderate impairment if CLcr (rounding to the nearest integer) is 30-59 mL/min
- Severe impairment if CLcr (rounding to the nearest integer) is 15-29 mL/min

A subject with CLcr (rounding to the nearest integer) higher than or equal to 90 mL/min is categorized as having normal renal function.

Following screening and Day -1 procedures, eligible subjects will be confined to the study center beginning Day -1 until the completion of assessments on Day 6. Subjects will return 14 ( $\pm$ 1) days after last dose for an in-clinic follow up visit (ie, Day 15).

The study schema is shown in [Figure 1-2](#).

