### **3.7. Visit Windows**

#### **3.7.1. Definition of Predose, Postdose, Study Day**

Predose value is defined as the last available value off-treatment collected prior to study drug administration.

Postdose value is defined as any value collected after the study drug administration and before the dosing date plus 30 days.

Study Day will be calculated from the date of GS-9876 administration and derived as follows:

- For postdose study days: assessment date – dosing date + 1
- For days prior to the dose: assessment date – dosing date

Therefore, study day 1 is the day of study drug administration.

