**Table 3-2. Predose and Postdose Visits of Laboratory Tests**

Visit Label	Study Day and Time points
Predose	-1
Day 1	1 (4 hours postdose)
Day 2	2 (chemistry and urinalysis only)
Day 3	3
Day 6	6
Follow-up	15 ( $\pm 1$ )
Early Termination	Early Termination (if applicable)

The predose and postdose visits for ECG for different cohorts are summarized in [Table 3-3](#).

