### 5.2. Baseline Characteristics

Baseline characteristics include body weight (in kg), height (in cm), and body mass index (BMI; in kg/m^2), CLcr (mL/min) using Cockcroft-Gault formula, and estimated glomerular filtration rate (eGFR) using the Modification of Diet in Renal Disease (MDRD) Study equation {[National Institute of Diabetes and Digestive and Kidney Diseases \(NIH\) 2016](#)}. The equation used for MDRD-based eGFR is as follows:

$$\text{eGFR (mL/min/1.73m}^2\text{)} = 175 \times (\text{S}_{\text{cr}})^{-1.154} \times (\text{Age})^{-0.203} \times (0.742 \text{ if female}) \times (1.212 \text{ if African American}),$$

where  $\text{S}_{\text{cr}}$  is serum creatinine in mg/dL.

These baseline characteristics will be summarized by renal function group (determined based on CLcr value from Cockcroft-Gault formula) using descriptive statistics (numbers of subjects, mean, SD, median, Q1, Q3, minimum, and maximum) for continuous variables and using the numbers and percentages of subjects for categorical variables. For baseline body weight, height, BMI, CLcr and eGFR, descriptive statistics also will be presented by sex in the same table. The summary of baseline characteristics will be provided for the Safety Analysis Set. No formal statistical testing is planned.

A by-subject listing of other baseline characteristics will be provided by subject ID number in ascending order.

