## 8.2. Statistical Analysis Methods

### 8.2.1. General considerations

Individual subject concentration data and individual subject PK parameters including percentage of protein binding for GS-9876 will be listed and summarized using descriptive statistics by renal function group. Summary statistics (numbers of subjects, mean, SD, coefficient of variation, median, minimum, maximum, Q1, and Q3) will be presented for both individual subject concentration data by time point and individual subject PK parameters by renal function group. Moreover, the geometric mean, 95% CI, and the mean and SD of the natural log-transformed values will be presented for individual subject PK parameter data.

Individual concentration data listings and summaries will include all subjects with concentration data. The sample size for each time point will be based on the number of subjects with nonmissing concentration data at that time point. The number of subjects with concentration BLQ will be presented for each time point. For summary statistics, BLQ values will be treated as zero at predose and one-half of the LLOQ for postdose time points.

Individual PK parameter data listings and summaries will include all subjects for whom PK parameter(s) can be derived. The sample size for each PK parameter will be based on the number of subjects with nonmissing data for that PK parameter.

In addition to the renal function categorization based on CLcr throughout this study, MDRD-based eGFR will be used for subject categorization in PK analysis. Subjects from all cohorts will be pooled and regrouped according to their MDRD-based eGFR values as follows:

- Normal renal function if eGFR (rounding to the nearest integer) is  $\geq 90$  mL/min/1.73m^2
- Mild impairment if eGFR (rounding to the nearest integer) is 60-89 mL/min/1.73m^2
- Moderate impairment if eGFR (rounding to the nearest integer) is 30-59 mL/min/1.73m^2

- Severe impairment if eGFR (rounding to the nearest integer) is 15-29 mL/min/1.73m^2
- End stage renal impairment if eGFR (rounding to the nearest integer) is  $\leq 14$  mL/min/1.73m^2

The following tables will be provided for GS-9876 by two sets of categorization (CLcr and MDRD-based eGFR) of renal function group:

- Individual subject concentration data and summary statistics
- Individual subject plasma PK parameters and summary statistics

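### Does the SAP need to name the visit whose creatinine sets the eGFR group?

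*SAP*

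**What the plan says.** The main grouping is by Cockcroft-Gault CLcr. SAP 1.3 fixes its timing: the category is assigned "using the Cockcroft-Gault formula from the screening visit".

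The second grouping is by MDRD eGFR. SAP 8.2.1 introduces it as an addition to the CLcr grouping: "Subjects from all cohorts will be pooled and regrouped according to their MDRD-based eGFR values as follows". Five bands follow, with eGFR rounded to an integer. Neither that section nor Table 8-3 names a visit, and the protocol synopsis, which lists the same bands apart from end stage, names none either. SAP 5.2 lists CLcr among the baseline characteristics, "and estimated glomerular filtration rate (eGFR) using the Modification of Diet in Renal Disease (MDRD) Study equation", and again gives no visit.

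More than one predose creatinine value exists. Protocol Table 6-1 schedules chemistry and creatinine clearance at Screening and Day -1, and Protocol 6.9.5.1 includes creatinine in the chemistry panel. On timing, the Table 6-1 footnote says "Prospective subjects should be screened no more than 28 days prior to administration of the first dose of study drug". Protocol 6.2.1 adds "Screening laboratory assessments may be repeated once within 28 days prior to administration of study drug to rule out laboratory error".

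Two other places bear on the choice. SAP 3.7.1 states "Predose value is defined as the last available value off-treatment collected prior to study drug administration", and Table 3-2 ("Predose and Postdose Visits of Laboratory Tests") places the laboratory predose visit on Day -1. Protocol 6.9.6 says "Weight will be collected at screening and upon admission to calculate creatinine clearance" and goes on to mention eGFR.

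**The concern.** A group that depends on an unnamed sample cannot be reproduced from the text alone. One analyst could carry screening over from the CLcr rule. Another could treat eGFR as a baseline laboratory value and take Day -1 under the predose definition. The SAP does not define baseline or link it to predose, so neither analyst breaks a written rule.

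The cut-off at 90 is the sensitive place. Controls are enrolled on CLcr, which is not indexed to body surface area, so a control can sit on either side of eGFR 90 and be counted as Normal on one sample and Mild on the other. All eGFR comparisons share the Normal group as reference, so one such move touches every row. SAP 8.2.2 runs a comparison only if each group has three or more subjects, so near that minimum the sample chosen could decide whether a row appears.

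Timing adds to the unease. The study is open-label and the SAP need be final only before database finalization, so the visit could be settled with PK results in view.

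**Working it through.** **The plan's own figure.** SAP 1.4 gives over 95% probability that the 90% CI lies within (50%, 200%), with 8 per group, log-scale SD 0.35 and true ratio 1.0. The exact power of two one-sided tests (14 df, bounds ±ln 2) is 96.6%, so the figure reproduces. It contains no eGFR term, and naming a visit leaves it unchanged.

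**Creatinine change needed to cross from Normal to Mild.** In the printed MDRD equation eGFR varies as creatinine^(−1.154). With rounding, Mild begins below 89.5. The rise needed from a starting value E is (E/89.5)^(1/1.154) − 1:

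| Starting eGFR | Rise needed |
|---|---|
| 91 | 1.5% |
| 92 | 2.4% |
| 95 | 5.3% |
| 100 | 10.1% |

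Example with assumed values (man, 60 years, 90 kg, factor 1.212 not applied):

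- Creatinine 0.85 mg/dL: eGFR = 175 × 0.85^(−1.154) × 60^(−0.203) = 91.9, Normal. CLcr = (80 × 90)/(72 × 0.85) = 117.6.
- Creatinine 0.88 mg/dL: eGFR = 88.3, Mild. CLcr = 113.6.

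He is a CLcr control on both samples.

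**How likely such a rise is.** The documents give no within-subject creatinine variability, so this part is assumption only. Take two independent log-normal samples around one level, each with the stated CV. The log difference has SD of about CV × √2, and P(rise ≥ r) = 1 − Φ[ln(1 + r)/(CV√2)]:

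| Assumed CV | Rise ≥ 5.3% | Rise ≥ 10.1% |
|---|---|---|
| 3% | 11% | 1% |
| 5% | 23% | 9% |
| 8% | 32% | 20% |

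A move by someone near the cut-off is therefore plausible, but its frequency cannot be fixed from the documents.

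**Effect of one move on the ratio.** Let one of n Normal subjects, k SDs from the mean, move into a Mild group of m, with the ratio otherwise 1.00. The Normal log-mean changes by −0.35k/(n − 1) and the Mild log-mean by +0.35k/(m + 1).

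- n = m = 8, k = 1: Mild/Normal = exp(0.35/9 + 0.35/7) = 1.09. Every other ratio to Normal is multiplied by exp(0.35/7) = 1.05.
- n = m = 8, k = 2: 1.20 and 1.11.
- n = 8, m = 3, k = 1: exp(0.35/4 + 0.35/7) = 1.15. For k = 2 it is 1.32.

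Subjects below the mean shift the ratio downward: for n = m = 8, to 0.92 at −1 SD and 0.84 at −2 SD.

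**Compared with the interval.** Using the pooled-variance t interval of the sample-size section, the 90% limits lie a factor exp(t × 0.35 × √(1/a + 1/b)) either side of the estimate, for group sizes a and b.

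- 8 and 8: exp(1.761 × 0.35 × 0.500) = 1.36.
- 7 and 9, after the move: exp(1.761 × 0.35 × 0.504) = 1.36.
- 8 and 3: exp(1.833 × 0.35 × 0.677) = 1.54. After the move, 7 and 4: exp(1.833 × 0.35 × 0.627) = 1.50.

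Each shift above is smaller than the factor that the data already carry.

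**Which sample the text favours.** For Screening:

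- SAP 1.3 uses it for renal categories, and SAP 8.2.1 adds eGFR as a second set of the same categories.
- The protocol synopsis gives the eGFR bands under eligibility.
- SAP 5.2 lists eGFR beside CLcr, which is grouped at screening, and height, which is measured only then.

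For Day -1 there are SAP 3.7.1 and Table 3-2. These belong to the visit-window rules, which serve summaries by visit and change from predose. Protocol 6.9.6 helps little, because its subject is the collection of weight and the MDRD equation has no weight term. Since Screening is at most 28 days before dosing and Day -1 is one day before, the samples are at most 27 days apart.

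**The case for a change.** The strongest case for a change is that the SAP specifies rounding and five bands for eGFR and the visit for CLcr, yet leaves out the one item that decides which creatinine value enters. Its general predose rule points away from the CLcr rule. Two competent programmers could produce different tables, one sentence would prevent that, and it would also keep the two groupings on one sample so that they differ only by formula.

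The factual part stands: no visit is named, two values exist, and a small difference can move a subject. A sentence would do no harm.

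It does not follow that the plan is in error. A written Day -1 rule would be as acceptable as a written screening rule, so the gap is one of convention and not of validity. Both samples are taken before dosing, so neither is affected by the drug. The possibility of choosing with results in view applies to any unwritten convention; here it reaches only a supplementary table, and the documents give no sign of it. SAP 8.2.2 speaks of impaired subjects against healthy controls, which does not fit the eGFR rows literally, but Table 8-3 defines each eGFR test and reference group, so nothing is left open there.

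**Conclusion.** No change follows. This is missing detail that an analyst would fill sensibly, most naturally with the screening sample already used for CLcr. Either sample gives a legitimate eGFR comparison, and no instruction in the SAP leads to a wrong result.

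The reach is limited to the tables, figures and comparisons by eGFR group. The CLcr comparisons stay tied to screening. The rule for opening Cohorts 2 and 3 and the sample-size statement (96.6% against the stated figure of over 95%) are untouched.

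In size, one subject 1 SD above the mean moving between groups of 8 shifts Mild/Normal from 1.00 to 1.09, against 90% limits a factor of about 1.36 away. Larger shifts need an extreme subject, very small groups, or several moves at once. These figures assume the planning SD of 0.35, a pooled-variance interval and a single move. The SAP's model allows a separate variance for each group, so its actual interval will differ somewhat. How often subjects would change group rests on a creatinine variability that the documents do not supply.

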### **8.2.2. Statistical Methodology**

The statistical comparisons of the natural log-transformed PK parameters for GS-9876 between renal impaired subjects and healthy controls will be performed. All subjects with available data for the PK parameter under evaluation will be included in the modeling.

Consistent with using two sets of renal function categorization in PK summaries, two corresponding sets of comparisons will be performed. Details of these comparisons are shown in [Table 8-3](#). To ensure the appropriateness of applications of statistical testing, the comparisons will only be implemented when there are at least 3 subjects in both test and reference groups. The ratio of geometric least squares means (GLSMs) for the PK parameter in comparison between the test and reference groups and the 90% CI for the ratio will be provided.

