## PHARMACOKINETIC ABBREVIATIONS AND DEFINITIONS

$AUC_{last}$	area under the plasma/serum concentration versus time curve from time zero to the last quantifiable concentration
$AUC_{inf}$	area under the plasma/serum concentration versus time curve extrapolated to infinite time, calculated as $AUC_{last} + (C_{last}/\lambda_z)$
$\%AUC_{exp}$	percentage of AUC extrapolated between $AUC_{last}$ and $AUC_{inf}$
$C_{max}$	maximum observed plasma/serum concentration of drug
$C_{last}$	last observed quantifiable plasma/serum concentration of the drug
$CL/F$	apparent oral clearance after administration of the drug: $CL/F = Dose/AUC_{inf}$ , where “Dose” is the dose of the drug
$\lambda_z$	terminal elimination rate constant, estimated by linear regression of the terminal elimination phase of the log plasma/serum concentration of drug versus time curve of the drug
$T_{max}$	time (observed time point) of $C_{max}$
$T_{last}$	time (observed time point) of $C_{last}$
$t_{1/2}$	estimate of the terminal elimination half-life of the drug in plasma/serum, calculated by dividing the natural log of 2 by the terminal elimination rate constant ( $\lambda_z$ )
$V_z/F$	apparent volume of distribution of the drug
$A_e$	Amount of unchanged drug excreted in urine calculated either over a specific interval ( $A_{e(interval)}$ ) or cumulatively over all collection intervals, calculated as (Concentration of unchanged drug in urine) · (Volume of urine collected)
$CL_r$	The renal clearance of unchanged drug in a specific interval ( $CL_{r(interval)}$ ) or cumulatively over all collection intervals
$\% Dose_{excreted}$	The percentage of given dose excreted in the urine as unchanged drug

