### 1.3. Study Design

Study GS-US-379-1932 is an open-label, parallel-group, adaptive, single-dose, multi-center Phase 1 study to evaluate the PK of GS-9876 in subjects with impaired renal function.

This study will target enrolling 20 to 60 subjects using an adaptive design that includes up to 3 enrolled cohorts of subjects with renal impairment and matched healthy controls. Based on safety and PK results from subjects with moderate renal impairment (Cohort 1), subjects with severe renal impairment (Cohort 2) and/or mild renal impairment (Cohort 3) will be enrolled as follows:

[figure not shown]
- Cohort 1 (Moderate Renal Impairment): Up to 20 subjects (10 per group, moderate renal impairment and matched healthy controls) for 8 evaluable subjects per group.
- Adaptive Cohort 2 (Severe Renal Impairment): Up to 20 subjects (10 subjects with severe renal impairment and up to 10 matched healthy control subjects if none of the healthy subjects from a previous cohort is an appropriate match for a severe impairment subject) for 8 evaluable subjects per group.

- Adaptive Cohort 3 (Mild Renal Impairment): Up to 20 subjects (10 subjects with mild renal impairment and up to 10 matched healthy control subjects if none of the healthy subjects from a previous cohort is an appropriate match for a mild impairment subject) for 8 evaluable subjects per group.

Adaptive Cohorts 2 and/or 3 will be enrolled as determined by safety and/or PK data in Cohort 1. Specifically, Cohort 2 (Severe Renal Impairment) will be evaluated if supported by safety and/or PK data from Cohort 1 (Moderate Renal Impairment). Cohort 3 (Mild Renal Impairment) will be evaluated if supported by safety and if substantial changes ( $\geq 2$ -fold mean difference from matched controls) in the exposure of GS-9876 is observed in subjects with moderate renal impairment in Cohort 1. Cohorts 2 and 3 may not be enrolled or may be enrolled sequentially or in parallel, as governed by safety and PK data in Cohort 1. Each control subject may be matched to multiple renal impaired subjects across different cohorts and can be matched to only 1 renal impaired subject within a cohort.

An overview of the study design is shown in [Figure 1-1](#).

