#### **1.4. Sample Size and Power**

With 16 (8 per group) evaluable subjects, the estimated two-sided 90% CI of the GLSM ratio of test versus reference groups, with regards to PK parameters (AUC and  $C_{\max}$ ) would be within (50%, 200%) with over 95% probability. This calculation is based on a two group t-test of equivalence in means at the significance level of 0.05, assuming the expected geometric means ratio of 1.0 and inter-subject standard deviation (SD) of no more than 0.35 on a natural logarithm scale. The assumption about the inter-subject SD is supported by previous Gilead study GS-US-379-1372 using the maximum variability for AUC and  $C_{\max}$  from the closest dose levels (15 mg and 30 mg) of the dose in this study. An overage of 2 subjects per group will be enrolled to accommodate subject drop-outs, thus requiring a total enrollment of 20 subjects (10 per group) for each cohort.

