##### **3.1.3. Pharmacokinetic Analysis Set**

The PK Analysis Sets include all enrolled subjects who took study drug and have at least 1 nonmissing postdose concentration value reported by the PK laboratory for the corresponding analytes. These are the primary analysis sets for all PK analyses.

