The following figures will be provided for GS-9876 by two sets of categorization of renal function group:

- Mean ( $\pm$  SD) concentration data versus time (on linear and semilogarithmic scales)
- Median (Q1, Q3) concentration data versus time (on linear and semilogarithmic scales)

A figure of individual subject concentration data versus time (on linear and semilogarithmic scales) will be provided.

Individual, mean, and median postdose concentration values that are  $\leq$  LLOQ will not be displayed in the figures and remaining points will be connected.

The following listings will be provided:

- Pharmacokinetic sampling details by subject, including differences in scheduled and actual draw times, and sample age
- Individual data on determination of plasma half-life and corresponding regression correlation coefficient

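### SAP 8.2.2 models every available AUClast with no minimum profile, so a subject who leaves while drug is still measurable biases a primary ratio; unlikely, modest and cheap to fix

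*SAP*

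**What the plan says.** AUClast, AUCinf and Cmax are the primary parameters (SAP 1.2 and 8.1.1). The SAP's pharmacokinetic definitions run AUClast "from time zero to the last quantifiable concentration", so its end point is each subject's own.

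Three inclusion rules follow:
- PK Analysis Set (SAP 3.1.3): subjects who took study drug and "have at least 1 nonmissing postdose concentration value reported by the PK laboratory for the corresponding analytes".
- Summaries (SAP 8.2.1): "Individual PK parameter data listings and summaries will include all subjects for whom PK parameter(s) can be derived".
- Primary ANOVA (SAP 8.2.2): "All subjects with available data for the PK parameter under evaluation will be included in the modeling". The only minimum there is 3 subjects per group, which counts subjects, not samples.

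Each cohort is planned "for 8 evaluable subjects per group" (SAP 1.3), and "An overage of 2 subjects per group will be enrolled to accommodate subject drop-outs" (SAP 1.4). Evaluable is not defined in either document. Protocol 4.1 allows replacement, with sponsor approval, of subjects who do not finish the intensive PK procedures, but not of those who leave for a drug-related AE. It does not say what happens to a replaced subject's data.

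**The concern.** AUClast can be derived from a partial profile. A subject who leaves at 24 h contributes roughly AUC0-24 beside other subjects' AUC0-120. The shortfall has one direction, because the truncated area cannot exceed the full one. In the impaired group it understates an increase in exposure, which is the effect the study is looking for. In a control it overstates one, possibly in more than one comparison: "Each control subject may be matched to multiple renal impaired subjects across different cohorts" (SAP 1.3).

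No binding safeguard covers this:
- The PK scientist's review of individual profiles in SAP 8.1 is written for AUCinf, lambda-z and half-life, which depend on the terminal phase. AUClast is not named.
- SAP 4.3 lets a deviation lead to exclusion but gives no criterion. Protocol 6.7 permits stopping at the subject's request, and the documents do not say whether that counts as a deviation.
- The sensitivity analysis in SAP 8.3 is optional and leaves the primary estimate unchanged.

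**Working it through.** **1. The plan's own figure.** Inputs from SAP 1.4: 8 per group, true ratio 1.0, log-scale SD 0.35, 90% CI, limits 50% and 200%. The exact two one-sided tests calculation (pooled SD, 14 df) gives P = 0.966, where P is the probability that the 90% CI lies within the limits. This agrees with the stated figure of over 95%. With 10 per group P = 0.991. The sample-size statement is not in error; it presumes complete values.

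**2. Fraction of the area retained.** The last plasma sample is at 120 h (SAP 1.3). The documents give no half-life, so I assume a one-compartment oral model with ka = 0.7/h and a range of half-lives. With k = ln 2 / half-life,

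A(T) = (1 − e^(−kT))/k − (1 − e^(−ka·T))/ka, and f = A(T)/A(120).

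Example, half-life 24 h and exit at 24 h: k = 0.02888; A(24) = 17.31 − 1.43 = 15.88; A(120) = 33.54 − 1.43 = 32.11; f = 0.495.

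| Half-life | f, exit 24 h | 48 h | 72 h | 96 h |
|---|---|---|---|---|
| 12 h | 0.728 | 0.933 | 0.984 | 0.997 |
| 24 h | 0.495 | 0.764 | 0.899 | 0.966 |
| 30 h | 0.434 | 0.704 | 0.860 | 0.949 |
| 48 h | 0.339 | 0.597 | 0.780 | 0.909 |

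**3. Effect on the geometric mean.** With m truncated values among n, the group mean is multiplied by f^(m/n).
- One of 10 at 24 h: 0.728^0.1 = 0.97; 0.495^0.1 = 0.93; 0.434^0.1 = 0.92.
- Two of 10 at 24 h: 0.94, 0.87, 0.85.
- Two of 10 at 72 h: 0.984^0.2 = 0.997 (12 h) to 0.860^0.2 = 0.970 (30 h), a shift of 3% or less.
- Two of 10 at 96 h: 0.949^0.2 = 0.990 (30 h); 0.909^0.2 = 0.981 (48 h).

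**4. Effect on the interval.** I simulated 300,000 trials per case: 10 per group, SD 0.35, true ratio 1, separate group variances with Satterthwaite df (close to the SAP's PROC MIXED code), truncation in the impaired group.

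| Case (exit at 24 h) | Half-life | Ratio | Coverage | P |
|---|---|---|---|---|
| No exit | – | 1.00 | 90% | 99% |
| One of 10 | 12 h | 0.97 | 90% | 99% |
| One of 10 | 24 h | 0.93 | 90% | 97.5% |
| One of 10 | 30 h | 0.92 | 90% | 96.5% |
| Two of 10 | 12 h | 0.94 | 89% | 98% |
| Two of 10 | 24 h | 0.87 | 85% | 92% |
| Two of 10 | 30 h | 0.85 | 84% | 88% |

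**5. Excluding instead.** If exit is unrelated to exposure, 8 against 10 complete profiles gives ratio 1.00, coverage 90% and P 98%. As an extreme bound, suppose the leavers are the highest exposures. Excluding one then gives 0.94 with coverage 86%; excluding two gives 0.895 with 80%. Keeping one such subject cut at 24 h gives 0.97 (12 h) to 0.92 (30 h). The break-even is f = 0.942^10 = 0.55, a half-life of about 20 h. Below that, exclusion is the more biased choice in this bound.

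**6. A truncated control.** SAP Table 8-3 names the reference only as normal renal function and does not say whether controls are pooled. Among 10 controls, one 24 h exit raises the ratio by a factor of 1/0.969 = 1.03 to 1/0.920 = 1.09. Among 20 to 30 pooled controls the control mean is multiplied by 0.434^(1/20) = 0.96 to 0.728^(1/30) = 0.99, so the ratio rises by about 1% to 4%.

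**The case against.** The strongest reply is that this will rarely happen and would be noticed. There is one dose, confinement lasts to Day 6 and covers every sample (Protocol 3.3), and Protocol 8.3 expects little missing data. AUCinf is co-primary and its profiles are reviewed, so a distorted AUClast ratio would sit beside an AUCinf ratio that disagrees with it. Tlast and %AUCexp are reported, and the SAP 8.2.1 listings include "Pharmacokinetic sampling details by subject, including differences in scheduled and actual draw times, and sample age". All of this stands and sets the severity. None of it corrects the AUClast ratio.

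A second reply is that modelling all available data is a rule stated in advance, and that exclusion can introduce selection. This also stands: step 5 shows that neither analysis is safe if leaving is related to exposure. It is why the two should be reported together.

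Third, a completeness cut-off taken from healthy volunteers could fail where it matters. At a 12 h half-life, 95% of AUC0-120 is reached by 53 h. If impairment doubled the half-life to 24 h, 53 h would capture only 80%, and two of 10 leavers would shift the mean by 1 − 0.80^0.2 = 4.4%. The fix has to allow for this.

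A reader might infer that a replaced subject's short profile is known to stay in the model. It follows from the wording of SAP 8.2.2, but Protocol 4.1 is silent, so it is an inference.

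**Conclusion.** The point holds as a gap of low severity. As written, SAP 8.2.2 biases the AUClast ratio whenever a subject leaves while drug is still measurable, and nothing binding prevents it. One early exit of 10 shifts the expected ratio by 3% to 8% without loss of coverage and with P above 95%. Two in the same group at about 24 h shift it by 6% to 15%, with coverage down to 84% and P down to 88% at the longest half-life considered. Exits at 72 h or later hardly matter at half-lives up to 30 h.

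These sizes rest on an assumed one-compartment model with half-lives of 12 to 30 h, 10 subjects per group and SD 0.35. The direction does not depend on the model.

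A reader might conclude that the primary PK result is unreliable or the trial undersized. The documents do not support that: the sample-size figure reproduces, Cmax is unaffected once the peak has been sampled, AUCinf has its own review, and material damage needs two early exits in one group together with a long half-life. Nor can one say that the decision on Cohort 3 would be distorted, since the two-fold criterion in SAP 1.3 refers to exposure without naming a parameter.

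**What to change.** Add one paragraph to SAP 8.2.2 before profiles are reviewed:
- AUClast enters the primary ANOVA only if sampling reached a late nominal time, the same for all groups, or concentrations had already fallen below quantitation.
- Do not set that time from healthy-volunteer half-life alone, because impairment may lengthen it. The 96 h sample is one workable choice: two of 10 leavers at 96 h shift the mean by about 1% at a 30 h half-life and 1.9% at 48 h.
- A replaced subject's incomplete AUClast is not in the primary model.
- Excluded profiles are listed with reasons, marking exits for drug-related AEs.
- The all-available analysis is a prespecified sensitivity analysis, reported beside the primary.

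AUCinf and Cmax stay as planned.

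The cost is an occasional exclusion, which the overage absorbs (8 against 10 gives P of 98% instead of 99%), and possible selection if leavers have high exposure (the bound in step 5). The paired analysis and the listed reasons would bring such selection to light.
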